Statistical analysis

Project title: Micronutrient Supplementation for Women With PCO-syndrome - Influence of Nutrition and Physiology on the Development of PCOS-typical Parameters

NCT number: N/A

Participants

Investigator:

Assoc.[name].Doiz. [name]

Participating doctors

Assoc.[name].Doiz. [name]

Participating clinics

Medical University of Vienna
Department of Obstetrics and Gynecology
Clinical Division of Gynecologic Endocrinology and
Reproductive Medicine
[name]
[name]
Tel: [name]
Fax: [name]

Sample size calculation:

Assuming a reduction of the mean AMH levels by 2 ng/ml at a standard deviation of 3 ng/ml and an alpha value of 0.05 and a power of 0.90, the paired t-test requires 26 patients per group. Due to the fact that the participants wish to conceive a child and have been diagnosed with sterility, a low drop-out rate can be expected. There is no reliable data on this or similar treatments that allow prediction of the chance to conceive. Due to the favourable benefit-to-risk profile, a 15% drop-out rate is assumed. This corresponds to 4 patients per group. Thus, the final sample size is calculated as 30 patients per group, which leads to a total study population of 60.

Parameters obtained during routine clinical examinations:

All parameters on outcome (AMH = anti-müllerian hormone, total testosterone and androstendion levels) will be obtained during routine clinical examinations.

Several additional parameters will also be collected and included in the database. They do not require additional effort on behalf of the patients. They include: general patient information (age, duration of infertility, height and body weight, additional medication); information pertaining to PCO-syndrome (menstruation history, Ferriman-Gallwey-score on hirsutism (if applicable), acne, scalp-hair effluvium); hormone parameters on days 2 to 5 of the menstrual cycle (androstendion, thyroid-stimulating hormone, luteal hormone, follicle-stimulating hormone, sex hormone binding globulin); as well as an oral glucose tolerance test, which is routinely performed by general practitioners.

In addition, the individual development of the fertility treatment will be documented for a maximum of 6 months following active study participation.

The bio-statistician will randomise the data using nQuery advisor™ Version 7.0. The information will then be packaged in an envelope by a person independent of the participating medical professionals and other scientific personnel. This will only be opened after the inclusion of the patient. Categorical variables will be presented as absolute numbers and percentages, numerical variables as median and interquartile range.

Final statistical analysis:

The following statistical analyses are planned: The result parameters and the patient characteristics of the two groups will be compared using the Welch test (for numerical variables) and the Chi-square-test or Fisher's exact test (for categorical variables). A p-value of <0.05 is considered to be statistically significant. The analysis will be performed as an intention-to-treat analysis. The statistical analyses will be performed using SPSS 24.0 for Windows (SPSS Inc., 1989-2017).

Overview on parameters to be analysed:

Parameter	Unit	Type	Planned statistical test
Age	Years	Numerical	Welch test
Body mass index	Kg/m ²	Numerical	Welch test
Sterility: Secondary (versus primary)	n (%)	Categorical	Chi-square/Fisher's exact test
Duration of infertility	Years	Numerical	Welch test
Pre-treatment FSH	mU/mL	Numerical	Welch test
Pre-treatment LH	mU/mL	Numerical	Welch test
Pre-treatment AMH	ng/mL	Numerical	Welch test
Pre-treatment testosterone	ng/mL	Numerical	Welch test
Pre-treatment androstenedione	ng/mL	Numerical	Welch test
Post-treatment AMH	ng/mL	Numerical	Welch test
Post-treatment testosterone	ng/mL	Numerical	Welch test
Post-treatment androstenedione	ng/mL	Numerical	Welch test

Abbreviations used: n (%) = number (frequency)

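### The 90% power is calculated for a paired t-test, but the SAP compares post-treatment AMH between groups with a Welch test, so the stated power does not apply to the planned analysis

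*SAP*

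**What the plan says.** Under *Sample size calculation*, the SAP takes "Assuming a reduction of the mean AMH levels by 2 ng/ml at a standard deviation of 3 ng/ml" and concludes that with "an alpha value of 0.05 and a power of 0.90, the paired t-test requires 26 patients per group". It then allows for dropout ("Due to the favourable benefit-to-risk profile, a 15% drop-out rate is assumed", counted as 4 patients per group) and ends with: "Thus, the final sample size is calculated as 30 patients per group, which leads to a total study population of 60".

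Under *Final statistical analysis*, the test is a different one: "The result parameters and the patient characteristics of the two groups will be compared using the Welch test" for numerical variables. The table *Overview on parameters to be analysed* lists "Post-treatment AMH" with the Welch test. The SAP contains no paired test, no change-from-baseline variable and no baseline-adjusted comparison.

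**The concern.** A paired t-test asks whether AMH changes from before to after treatment in the same women. A Welch test on post-treatment values asks whether two independent groups differ. The second carries the sampling error of two means, so at the same standardised effect it needs roughly twice as many patients per group. The SAP sizes the trial for the first question and analyses the second.

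Two inputs needed to carry the power across are also undefined:

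- **The SD.** The SAP does not say whether 3 ng/ml is the SD of the AMH level, which the post-treatment Welch test uses, or of the paired change, which the paired t-test uses.
- **The effect.** A 2 ng/ml fall in mean AMH equals a 2 ng/ml between-group difference only if the control mean does not change.

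AMH is the only variable behind the total of 60. A null AMH result would be read as coming from a trial with 90% power when that has not been shown.

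**Working it through.** **Inputs from the SAP.** Effect 2 ng/ml, SD 3 ng/ml, alpha 0.05, power 0.90, 30 per group randomised, 30 − 4 = 26 per group after dropout. Sidedness is not stated. Two-sided is assumed because it reproduces the SAP's 26 (one-sided gives 21).

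**Step 1: the SAP's own figure.** Paired t-test: noncentral t with n − 1 degrees of freedom and noncentrality (2/3)·√n.

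- n = 25: power 0.892
- n = 26: noncentrality 0.667 × 5.099 = 3.40, power 0.904

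The smallest n is 26, so the SAP's figure is reproduced exactly, with 3 ng/ml entering as the SD of the paired differences.

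**Step 2: the planned test, with SD 3 for the compared values and an unchanged control mean.** Two-sample t: 2n − 2 degrees of freedom and noncentrality (2/3)·√(n/2).

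| n per group | Noncentrality | Power | Simulated Welch test (100,000 runs) |
|---|---|---|---|
| 26 | 2.40 | 0.654 | 0.653 |
| 30 | 2.58 | 0.719 | 0.719 |
| 48 | 3.27 | 0.898 | – |
| 49 | 3.30 | 0.904 | 0.905 |

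90% power needs 49 evaluable per group. With 15% dropout, 49/0.85 = 57.6, so 58 randomised per group; adding 15% on top, as the SAP does, gives 49 × 1.15 = 56.4, so 57. The difference detectable with 90% power is 2.75 ng/ml at 26 per group and 2.55 ng/ml at 30.

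**Step 3: the SD that would justify 90%.** Solving the same formula for the SD at a 2 ng/ml difference gives at most 2.18 ng/ml (26 per group) or 2.35 ng/ml (30 per group).

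**Step 4: SD 3 read as the SD of the change.** With equal pre- and post-treatment SDs and correlation r, the post-treatment SD is 3/√(2(1 − r)). The SAP gives no r, so a range is shown.

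| r (assumed) | Post-treatment SD | Power, 26 per group | Power, 30 per group |
|---|---|---|---|
| 0 | 2.12 | 92% | 95% |
| 0.1 | 2.24 | 89% | 93% |
| 0.2 | 2.37 | 85% | 89% |
| 0.3 | 2.54 | 80% | 85% |
| 0.5 | 3.00 | 65% | 72% |
| 0.7 | 3.87 | 45% | 50% |
| 0.8 | 4.74 | 32% | 36% |

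Power reaches 90% only for r up to 0.05 (26 per group) or 0.18 (30 per group).

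**Step 5: the control assumption.** For illustration only, with SD 3 and 26 per group: if the control mean falls by 0.5 ng/ml, the difference is 1.5 ng/ml and power is 42%; if it falls by 1.0 ng/ml, the difference is 1.0 ng/ml and power is 22%.

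**The case against.** The best counter-argument is that 65% is one point in a wide range. The paired calculation makes sense only if 3 ng/ml is the SD of the change, and on that reading the Welch power at 26 per group can be as high as 92%. This stands as a caution about the figure: 65% holds if SD 3 applies to the compared values, or if r happens to be 0.5. It does not rescue the 90%, which would require pre- and post-treatment AMH in the same woman to be almost uncorrelated, an assumption the SAP does not state. Applying the Welch test to change scores with SD 3 does not help either: the calculation is that of step 2, and power is again 65%.

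Three smaller points are fair:

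- The SAP never calls the sizing comparison within-group. That is inferred from the test named and from 26 being exactly the paired answer.
- The protocol is not at hand and might plan a further AMH analysis. Both conflicting statements are nevertheless in this SAP, and another analysis would not give the Welch test the power of a paired test.
- An intention-to-treat analysis might keep all 30 per group. Power with SD 3 is then 72%, still short.

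A one-sided 0.05 test would give 77% at 26 per group, also short, and would no longer reproduce the SAP's 26.

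**Conclusion.** The concern holds. The SAP's 26 per group is right for a paired t-test and does not support the between-group Welch test it plans. That conclusion does not depend on which SD is meant.

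The size of the shortfall does depend on it. With SD 3 for the compared values, a true between-group difference of 2 ng/ml and two-sided 0.05, power at 26 per group is about 65%, so such a difference would be missed about one time in three. With SD 3 for the change, the shortfall runs from none at r near 0 to very large at high r. Both readings assume equal SDs in the two groups and an unchanged control mean. The mismatch must be corrected, because this calculation is the SAP's only justification for its sample size.

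**What to change.** In *Sample size calculation*, replace the paired t-test statement with a two-sample calculation for the planned comparison of post-treatment AMH:

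1. State whether 3 ng/ml is the SD of the level or of the change and, if of the change, the assumed pre/post correlation.
2. State that 2 ng/ml is the between-group difference, and what change is assumed in the control group.
3. Keep 60 patients and restate the power, for example:

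> With 30 randomised and 26 evaluable per group, a two-sided Welch test at the 0.05 level has X% power for a between-group difference of 2 ng/ml in post-treatment AMH, assuming an SD of Y ng/ml.

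X follows from Y: about 90% for Y = 2.18, 80% for 2.54, 65% for 3 and 45% for 3.87. If Y = 3, the SAP could instead state 90% power for a difference of about 2.75 ng/ml.

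An option at the same sample size is to pre-specify a baseline-adjusted comparison, since pre-treatment AMH is already collected. Its residual SD is roughly the level SD × √(1 − r²). With level SD 3 and r = 0.7 this is 3 × 0.714 = 2.14, giving about 91% power at 26 per group; with r = 0.5 it is 2.60, giving about 78%. If 3 ng/ml is the change SD and r = 0.7, it is 3.87 × 0.714 = 2.77, giving about 72%. The SD and r must be stated here too.

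Restating the power costs SAP wording only, with no additional patients. The sponsor must first define the SD, and should expect a figure below 90% for the Welch test unless the post-treatment SD is about 2.2 ng/ml or less. The baseline-adjusted option would also change the analysis section.

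### The drop-out allowance is slightly too small: 4 of 30 per group is 13.3%, not the stated 15%, and leaves an expected 25.5 completers where 26 are required

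*SAP*

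**What the plan says.** The relevant text is the SAP's paragraph headed Sample size calculation. The design inputs are "Assuming a reduction of the mean AMH levels by 2 ng/ml" "at a standard deviation of 3 ng/ml", with "an alpha value of 0.05 and a power of 0.90". From these the SAP concludes that "the paired t-test requires 26 patients per group".

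It then allows for losses: "a 15% drop-out rate is assumed. This corresponds to 4 patients per group". The result is that "the final sample size is calculated as 30 patients per group, which leads to a total study population of 60".

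The SAP does not show how 15% became 4 patients. It also does not say whether alpha is one- or two-sided, or whether the SD is that of the paired difference.

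**The concern.** A drop-out rate describes what happens to enrolled patients, so the allowance has to be checked against the number enrolled. The paragraph implies that 30 enrolled per group, less 15%, still gives the 26 needed for power 0.90. The three figures (15%, 4 and 30) do not agree. If 4 of 30 are lost, the rate is below 15%. If 15% of 30 are lost, fewer than 26 are expected to remain.

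What is at stake is the accuracy of a figure on which the recruitment target rests, and the method that would be reused if the sample size were recalculated.

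**Working it through.** **Inputs, all from the SAP's sample size paragraph.** Mean reduction 2 ng/ml; SD 3 ng/ml; alpha 0.05; power 0.90; 26 per group required; drop-out 15%; allowance 4; final size 30 per group, 60 in total.

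**Assumptions.** The SD is read as the SD of the paired difference, because a paired t-test is named. Alpha is taken as two-sided, because that reproduces the stated 26; one-sided gives 21.

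**Step 1: reproduce the 26.** The standardised effect is d = 2/3 = 0.667. Power of the paired t-test comes from the noncentral t distribution with n − 1 degrees of freedom and noncentrality d√n. The smallest n with power of at least 0.90 is 26, where power is 0.904; at n = 25 it is 0.892. The stated 26 is confirmed.

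**Step 2: reproduce the 30.** 26 × 0.15 = 3.9, which rounds to 4, and 26 + 4 = 30. This is the likely route to the stated figure: 15% of the completers, added on.

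**Step 3: check the 30 against the 15%.**
- Loss rate implied by 4 of 30: 4/30 = 13.3%.
- Patients lost at 15% of 30: 4.5.
- Expected completers: 30 × 0.85 = 25.5, below 26.

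**Step 4: enrolment that meets the requirement.** n/(1 − d), with d now the drop-out rate: 26/0.85 = 30.6, so 31 per group and 62 in total. Check: 31 × 0.85 = 26.35, at least 26. The difference from the SAP is 1 per group and 2 in total.

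**Step 5: size of the effect on the plan's own basis.** Completers are taken as binomial with probability 0.85. Mean power averages the Step 1 power over that distribution.

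| | 30 enrolled | 31 enrolled |
|---|---|---|
| Expected completers | 25.5 | 26.35 |
| Mean power at 15% drop-out | 0.896 | 0.906 |
| Chance that a group ends below 26 | 0.48 | 0.32 |

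Evaluating the power formula directly at 25.5 completers gives 0.898. So power at 15% drop-out from 30 is 0.896 to 0.898, depending on whether one averages over drop-out or uses its expectation, against 0.904 with exactly 26 completers.

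**The case against.** The strongest objection is that nothing practical follows. The shortfall is half a patient per group in expectation, and power of 0.896 to 0.898 still rounds to 0.90. The 15% is itself a planning guess: the SAP expects few losses and says it has no reliable data for predicting conception. All of this stands, and it keeps the point at the lowest severity. It does not make the sentence correct, since 15% and 4 of 30 remain different rates.

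A second objection is that the formula is inferred. The SAP does not say 15% of 26; 15% of 30 is 4.5, and rounding that down also gives 4. This is fair, so the cause is given above only as likely. The conclusion does not depend on it, because expected completers are 25.5 under either reading.

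A third objection is that dividing by 0.85 does not guarantee 26 completers either. That is also true: from 31 enrolled, a group still ends below 26 with probability 0.32. The 0.48 from 30 should be read only beside that figure.

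A reader might go further and infer that the trial is underpowered because of this slip, or that 62 patients must be recruited. The SAP's figures do not support either: the cost is about one percentage point of power or less. The mismatch between a sample size built on a paired test and the between-group Welch test planned under Final statistical analysis is a separate question and adds no weight here.

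**Conclusion.** The stated allowance is wrong as written, by a small margin. Thirty per group covers about 13% drop-out, and covering the assumed 15% in expectation would take 31 per group. Nothing elsewhere in the SAP repairs this. The intention-to-treat statement does not, because the plan itself adds patients to replace losses and the SAP gives no method for missing post-treatment values.

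The arithmetic on 4, 15%, 26 and 30 needs no assumption. The power figures rest on the SD being that of the paired difference, on a two-sided test and, for the averaged values, on independent drop-out at exactly 15%.

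**What to change.** Keep 30 per group and 60 in total, and replace the drop-out sentence with one saying that this allows for about 13% drop-out (4 of 30 per group), and that power on the stated paired-test basis would be just under 0.90 (about 0.896) if drop-out reached 15%. If the sample size is recalculated for any other reason, obtain the number to enrol as n/(1 − 0.15), rounded up.

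The cost is one sentence in the SAP. No extra patients are needed; the only change is a slightly less favourable statement of what 60 patients cover.

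### Does summarising the hormone outcomes by median and interquartile range clash with testing them by means, without a promised confidence interval?

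*SAP*

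**What the plan says.** Three statements in the SAP bear on this point.

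- **Description.** Directly before the heading Final statistical analysis, at the end of the paragraph on randomisation and envelopes, the SAP says: "Categorical variables will be presented as absolute numbers and percentages, numerical variables as median and interquartile range". No variable is singled out.
- **Testing.** Under Final statistical analysis: "The result parameters and the patient characteristics of the two groups will be compared using the Welch test" for numerical variables, with chi-square or Fisher's exact test for categorical ones. The parameter table lists the Welch test for post-treatment AMH, testosterone and androstenedione, and equally for age, body mass index and the pre-treatment hormones. The criterion is: "A p-value of <0.05 is considered to be statistically significant".
- **Sizing.** Under Sample size calculation the target is set on a mean: "Assuming a reduction of the mean AMH levels by 2 ng/ml at a standard deviation of 3 ng/ml", with "an alpha value of 0.05 and a power of 0.90", from which "the paired t-test requires 26 patients per group".

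The SAP does not name a mean, a standard deviation, a between-group difference or a confidence interval as something to be reported. It does not exclude any of them either.

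**The concern.** The design hypothesis and the test are about means, yet the only summary named for numerical variables is the median with its interquartile range. A report that gave only what is named would show two medians and a p-value for a difference in means that it never displays. A reader might subtract the medians and take the result for the tested effect. That reader would also not see which mean differences remain compatible with the data. This matters most for a non-significant result in a trial of 30 per group, where an interval could still include the target of 2 ng/ml. At stake would be the reported size and precision of the effect. The significance decision was never in question.

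**Working it through.** **1. The plan's own figure.** Inputs from Sample size calculation: difference 2 ng/ml, SD 3 ng/ml, alpha 0.05, power 0.90, paired t-test. Sidedness is not stated; two-sided is assumed.

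- Noncentrality at n = 26: (2/3) × √26 = 3.40, with 25 degrees of freedom. Power is 0.904, and 26 is the smallest n that reaches 0.90, so the stated figure reproduces.
- Drop-out: 26 × 0.15 = 3.9, taken as 4, and 26 + 4 = 30 per group.

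Nothing in this calculation depends on how the results are summarised.

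**2. What the test uses.** The Welch statistic is

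t = (mean₁ − mean₂) / √(s₁²/n₁ + s₂²/n₂).

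The 95% interval is (mean₁ − mean₂) ± t(0.975, df) × √(s₁²/n₁ + s₂²/n₂), with the same degrees of freedom. The same five ingredients (difference in means, two SDs, two group sizes) give the p-value and the interval. Whoever carries out the planned test therefore has the interval, and printing a median changes none of the ingredients.

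**3. How wide the interval would be.** The SAP does not say what the SD of 3 refers to. With equal SDs and equal group sizes:

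| Assumption | 26 per group | 30 per group |
|---|---|---|
| SD 3 for post-treatment AMH in each group: t × 3 × √(2/n) | 2.009 × 0.832 = 1.67 | 2.002 × 0.775 = 1.55 |
| Same, SD 2 to 4 | 1.11 to 2.23 | 1.03 to 2.07 |
| SD 3 for within-patient change, one group: t × 3/√n | 2.060 × 0.588 = 1.21 | 2.045 × 0.548 = 1.12 |

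On the first row, an observed difference of 1.0 ng/ml with 26 per group would carry an interval of 1.0 ± 1.67, about −0.7 to 2.7. These widths follow from n and SD alone. They are identical whether or not the SAP promises the interval, so they do not measure a cost of the wording.

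**4. Medians against means.** For two normal groups with SD 3 and a true difference of 2 ng/ml (200,000 simulated trials per sample size), the difference in medians minus the difference in means behaves as follows:

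- 26 per group: SD 0.584, 95% range −1.15 to 1.15, more than 0.5 ng/ml apart in 39.0% of trials.
- 30 per group: SD 0.549, 95% range −1.08 to 1.08, more than 0.5 ng/ml apart in 36.0% of trials.

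Both ranges are centred on zero. With symmetric data the two differences estimate the same quantity, so the gap is sampling noise and not bias.

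For skewed data, take a lognormal shape with SD 3 and assumed means of 8 and 6 ng/ml (the SAP gives no AMH level):

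- The median is mean/√(1 + 9/mean²).
- 8/√(1 + 9/64) = 7.49 and 6/√(1 + 9/36) = 5.37.
- The difference in medians is 7.49 − 5.37 = 2.12, against 2.00 in means.

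In either case the gap matters only if someone subtracts the medians and calls the result the tested effect. The SAP tells nobody to do that.

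**5. The sentences side by side.** The descriptive sentence pairs categorical with numerical variables in general and so covers age and duration of infertility as much as AMH. It precedes the section on the final analysis and says nothing about an effect measure. The testing sentence fixes the comparison. One describes the distribution in each group and the other compares the groups, so both can be followed at once without conflict.

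**The case for a change.** The strongest case for the concern runs as follows. Presentation and tests are proper SAP content, and this SAP chose to specify both. It named a median-based summary with no exception for outcomes, next to a test of means and a target stated as a mean. On the SD-3 reading, an interval half-width of 1.67 ng/ml is about 84% of the 2 ng/ml target (1.67/2), so precision is coarse and worth showing. One added sentence would also settle the reported effect measure before the data are seen.

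Part of this stands. The SAP indeed promises no interval, and reporting the mean difference with one would be good practice. The arithmetic is also right.

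What does not follow is that the document states something wrongly, contradicts itself or fixes something badly. Medians and interquartile ranges beside a Welch test are common and legitimate. The effect measure is not left open in any way that could alter the result, because the named test already concerns the difference in means. The coarse precision belongs to the sample size and would be the same with the sentence added. The protocol, which is not at hand, may also contain the reporting commitment.

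Sizing by a paired test while comparing two groups by the Welch test is a separate question. It neither supports this point nor is settled by it.

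**Conclusion.** The concern does not hold. Followed as written, the descriptive convention leaves the Welch test, its p-value and the significance decision unchanged, and the effect on sample size is nil: 26 evaluable and 30 enrolled per group either way. The interval that seems to be missing comes directly from the planned analysis and can be reported without amending anything.

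The figures of 1.67 and 1.55 ng/ml illustrate what that interval would look like if an SD of 3 ng/ml applied to post-treatment AMH in each group. They are not a loss caused by the plan. The median-versus-mean gaps are noise around zero under normality, and 2.12 against 2.00 ng/ml under one assumed skewed shape.

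This conclusion covers only the choice of summary and the absence of a promised interval. It rests on reading the median sentence as a description of each group, which its generic wording and its place before the final-analysis section support.

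### The between-group tests of AMH, testosterone and androstenedione ignore each hormone's pre-treatment value: valid, but imprecise unless the pre/post correlation is below about 0.2

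*SAP*

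**What the plan says.** Under Final statistical analysis, the SAP sets one rule for all numerical variables, outcomes and baseline characteristics alike: "The result parameters and the patient characteristics of the two groups will be compared using the Welch test (for numerical variables". The table headed Overview on parameters to be analysed applies it row by row. "Pre-treatment AMH" has its own Welch test, as do pre-treatment testosterone and androstenedione. "Post-treatment AMH", "Post-treatment testosterone" and "Post-treatment androstenedione" have theirs. No row is a change from baseline, and no model with a covariate is named.

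The SAP treats these three hormones as the outcomes. The sample size paragraph is about AMH: "Assuming a reduction of the mean AMH levels by 2 ng/ml at a standard deviation of 3 ng/ml", with a paired t-test, alpha 0.05 and power 0.90, giving 26 per group and 30 after dropout. The software is also fixed: "The statistical analyses will be performed using SPSS 24.0 for Windows".

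**The concern.** Each outcome hormone is measured before and after treatment, yet the earlier measurement is used only to ask whether the groups differed at the start. In a randomised trial that question says little. The useful role of the pre-treatment value is to remove between-woman variation from the treatment comparison, and the plan does not use it that way. Any chance difference between the groups at baseline also stays in the estimate.

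This is not a question of validity. The planned test is fixed in advance, is unbiased under randomisation and has the right type I error. What is at stake is the width of the confidence interval and the power of a trial of 60 women, given data it already intends to hold.

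**Working it through.** **Inputs.** From the SAP: difference 2 ng/ml, SD 3 ng/ml, alpha 0.05, 26 evaluable and 30 randomised per group. Assumed: the pre/post correlation r (not in the SAP, so varied), equal pre and post SDs, two-sided testing, and 2 ng/ml taken as the difference between groups.

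**The SAP's own figure.** A two-sided paired t-test with mean change 2 and SD 3 has exact power 0.904 at n = 26, so the stated 26 is reproduced. For dropout, 26 × 1.15 = 29.9 gives the stated 30; 26/0.85 = 30.6 would give 31. The SAP does not say whether SD 3 belongs to the values (reading A) or to the within-woman change (reading B, which a paired test implies). Both are shown.

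**Precision, reading A, 26 per group.**
- Welch half-width of the 95% CI: t(50) × 3 × √(2/26) = 2.009 × 0.832 = 1.67 ng/ml.
- ANCOVA half-width: t(49) × 3 × √(1−r²) × √[(2/26)(1 + 1/48)].
- Variance ratio, ANCOVA to unadjusted: (1−r²)(1 + 1/48).

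| r | Variance ratio | ANCOVA half-width (ng/ml) |
|---|---|---|
| 0 | 1.021 | 1.69 |
| 0.2 | 0.980 | 1.66 |
| 0.3 | 0.929 | 1.61 |
| 0.5 | 0.766 | 1.46 |
| 0.7 | 0.521 | 1.21 |

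At r = 0.5, 1/0.766 = 1.31, so adjustment is worth about 30% more women.

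**Break-even.** Setting (1−r²)(1 + 1/(2n−4)) = 1 gives r = 1/√(2n−3): 1/√49 = 0.143 at 26 per group and 1/√57 = 0.132 at 30. Between there and r = 0.2 the gain is at most about 2% of variance.

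**Power for a 2 ng/ml difference, 26 per group.** Simulated with 60,000 runs per cell, Monte Carlo standard error at most 0.002. The ANCOVA uses HC2 standard errors and a t reference with N−3 degrees of freedom. Under reading B the value SD is 3/√(2(1−r)), that is 2.54, 3.00, 3.87 and 4.74 at r = 0.3, 0.5, 0.7 and 0.8.

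| r | A: Welch | A: ANCOVA | B: Welch | B: ANCOVA |
|---|---|---|---|---|
| 0 | 0.655 | 0.647 | – | – |
| 0.1 | 0.653 | 0.649 | – | – |
| 0.2 | 0.653 | 0.664 | – | – |
| 0.3 | 0.65 | 0.69 | 0.80 | 0.82 |
| 0.5 | 0.65 | 0.77 | 0.65 | 0.77 |
| 0.7 | 0.65 | 0.90 | 0.45 | 0.72 |
| 0.8 | 0.65 | 0.97 | 0.32 | 0.69 |

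With 30 per group under A, Welch is about 0.72 and ANCOVA 0.75, 0.83, 0.94 and 0.99 at r = 0.3, 0.5, 0.7 and 0.8.

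**Choice of standard error.** Over r = 0 to 0.8 at 26 per group, type I error is 0.056 to 0.058 with HC0, 0.049 to 0.051 with HC2 and 0.042 to 0.044 with HC3. HC2 gives 0.047 to 0.048 with skewed (lognormal) data and 0.050 when one group's post-treatment SD is 0.7 times the other's. The power gain persists in both settings.

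**Chance imbalance, reading A.** The SE of the baseline AMH difference is 3√(2/26) = 0.832, so a difference of at least 1 ng/ml in either direction has probability 0.229; at 30 per group, SE 0.775 and probability 0.197. Such a difference shifts the unadjusted estimate by r × 1 ng/ml. Its variability is already inside the Welch standard error, so it illustrates the same loss and does not add to it.

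**The case against.** **Nothing is in error, and the benefit rests on an unknown r.** The planned test is clear, consistent and valid. No passage supports a high correlation, and at r = 0.3 power moves only from 0.65 to 0.69. This stands as a limit on what can be claimed: the size of the gain is uncertain. The payoff is lopsided, though. The worst case is about 2% more variance, against 23% less at r = 0.5 and 48% less at r = 0.7.

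**The ±1.67 and 23% figures use reading A, while a paired test implies reading B.** This is fair. Under B the Welch half-width is 1.67 × 2.54/3 = 1.41 at r = 0.3 and 1.67 × 3.87/3 = 2.16 at r = 0.7. The imbalance probability at 26 per group runs from about 16% (r = 0.3) to 45% (r = 0.8). The variance ratios and the break-even are the same under both readings.

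**The low Welch power comes mostly from sizing on a paired test.** This is also fair. That is a separate point and lends no weight here; the argument rests on the comparison of ANCOVA with Welch at the same n.

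**Robust standard errors are unnecessary with equal groups.** With equal numbers, ordinary ANCOVA and HC2 do agree: type I error is 0.048 to 0.054 against 0.049 to 0.053, and power is within 0.001. Dropout need not be equal, however. With 22 and 30 women and post-treatment SDs in ratio 0.7, ordinary ANCOVA has type I error between 0.040 and 0.064, depending on which group has the larger SD, against 0.050 to 0.054 for HC2. HC2 keeps the protection against unequal variances that the Welch test provides.

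**Conclusion.** The concern holds as a loss of precision. The plan collects a pre-treatment value for each outcome hormone and leaves it out of the treatment comparison. There is no bias and no type I error fault.

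The loss is negligible if r is below about 0.2 (exact break-even 0.13 to 0.14). Under reading A it is about 0.11 to 0.12 of power at r = 0.5 and 0.25 at r = 0.7. Under reading B it is about 0.12 and 0.27. These figures assume 26 evaluable women per group, equal pre and post SDs and a true between-group difference of 2 ng/ml. They are worked for AMH only; for testosterone and androstenedione the SAP gives no effect or SD, but the variance ratios apply to any r. The description of the plan is certain; the size of the gain is not. It should be fixed, because the change is cheap and has almost no downside.

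**What to change.** For each of AMH, testosterone and androstenedione, replace the post-treatment Welch test as the between-group test by an ANCOVA of the post-treatment value on group and the pre-treatment value of the same hormone. Use HC2 robust standard errors and a t reference with N−3 degrees of freedom, and report the adjusted difference with its 95% CI. Name HC2 explicitly, since HC0 and HC3 give different type I error at this size. Confirm that SPSS 24.0 provides it, or name software that does. Keep the Welch test on post-treatment values as a sensitivity analysis that cannot replace the ANCOVA.

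The cost is SAP wording, one degree of freedom per hormone, the software check, and under 0.01 of power if r is near zero. There are no new data and no burden on patients. A woman without a pre-treatment value would drop out of the ANCOVA but not out of the Welch test. As the SAP promises an intention-to-treat analysis, the wording must say how she is handled. This change does not repair the paired-test basis of the sample size.
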